**Proprietary confidential information.**

© 2016 Boehringer Ingelheim International GmbH or one or more of its affiliated companies. All rights reserved.

This document may not - in full or in part - be passed on, reproduced, published or otherwise used without prior written permission.

If a patient withdraws consent for any further trial procedures and follow-up activities, no additional study assessments will be completed. This will be documented in the eCRF.

#### 3.3.4.2 Discontinuation of the trial by the sponsor

Boehringer Ingelheim reserves the right to discontinue the trial overall or at a particular trial site at any time for the following reasons:

1. Failure to meet expected enrollment goals overall or at a particular trial site.
2. Emergence of any efficacy/safety information that could significantly affect continuation of the trial.
3. Violation of GCP, the CTP, or the contract by a trial site or investigator, disturbing the appropriate conduct of the trial.
4. The recommendation of the DMC that would require discontinuation of the trial, or the planned futility analysis response is not met.
5. Discontinuation of the clinical development programme with afatinib due to emerging data on afatinib.
6. The primary analysis has been completed and all patients have either ended study treatment or are eligible to receive afatinib under the conditions indicated in [3.3.4.1](#).

The investigator / the trial site will be reimbursed for reasonable expenses incurred in case of trial termination (except in case of the third reason).

## 4. TREATMENTS

### 4.1 TREATMENTS TO BE ADMINISTERED

Patients will be randomized to receive either afatinib or erlotinib.

#### 4.1.1 Identity of BI investigational product and comparator products

Substance (INN):	Afatinib
Pharmaceutical form:	Film-coated Tablet
Source:	Boehringer Ingelheim Pharma GmbH & Co. KG
Unit strength:	50 mg, 40mg, 30mg and 20mg film-coated Tablets (the dose of afatinib in the film-coated Tablets is related to the free base equivalent of afatinib)
Posology:	Once daily
Route of administration:	Oral (swallowed)

Substance (INN):	Erlotinib (Tarceva®)
Pharmaceutical formulation:	Film-coated Tablets
Source:	OSI Pharmaceuticals Inc. and Roche Ltd.
Unit Strength:	150 mg, 100mg, 25mg film-coated Tablets (the dose of strength of erlotinib hydrochloride of 163.9 mg, 109.3 mg and 27.3 mg is equivalent to erlotinib strengths 150 mg, 100 mg, and 25 mg, respectively)
Posology:	Once daily
Route of administration:	Oral (swallowed)

#### 4.1.2 Method of assigning patients to treatment groups

Patients will be randomised 1:1 to either afatinib or erlotinib. The randomisation will be stratified based on race (Eastern Asian vs. non-Eastern Asian), as specified in the [flow chart](#).

Randomisation will be carried out centrally using an Interactive Voice/Web Response System (IXRS). The company that provides the IXRS system will receive the randomisation list from Boehringer Ingelheim Clinical Trial Support Group or a CRO appointed by the Sponsor. The BI standard validated random number generating system will be used to generate the

**Proprietary confidential information.**

© 2016 Boehringer Ingelheim International GmbH or one or more of its affiliated companies. All rights reserved.

This document may not - in full or in part - be passed on, reproduced, published or otherwise used without prior written permission.

randomisation schedules which will be verified by an independent statistician who is not involved in the study. The access to the randomisation code will be supervised by Clinical Trial Support Group. Persons directly involved in the conduct and analysis of the trial have no access to the randomisation schedule prior to database lock.

Investigators and site staff delegated IXRS responsibilities will receive unique user IDs and passwords; and a manual describing how to access and use the IXRS.

#### 4.1.3 Selection of doses in the trial

Based on early phase clinical trials, a daily dose of 50 mg in the monotherapy setting was identified as the dose for further development. This was used initially in EGFR TKI refractory population and several other Phase II/III and proof of concept trials. Given a higher propensity of grade 3/4 AEs (especially diarrhoea) and no loss of efficacy especially in the EGFR mutation positive population, the dose was reduced to 40 mg in the pivotal Phase III trials in EGFR mutated population ([P10-12524](#), [P10-12525](#), [P10-12529](#)). The 1200.22 (LUX-Lung 2) study enrolled 99 patients who started afatinib at 50mg, and 30 patients starting at 40mg. While there was no substantial change in the occurrence of all AE grades for the two most frequent AEs, diarrhoea (96.7% in the 40 mg group compared to 93.9% in the 50 mg group) and rash/acne (90.0% in the 40 mg group compared to 92.9% in the 50 mg group); there was a substantial difference in the occurrence of grade 3 AEs for diarrhea (6.7% in the 40 mg group vs 24.2% in the 50mg group) and rash/acne (6.7% in the 40 mg group and 25.3% in the 50 mg group). Neither group had grade 4 or 5 AEs reported for these terms (P10-12524). Refer to the current IB for additional details ([U03-3218](#)). In NSCLC and other indications, durable responses (>20 months) have been observed with daily dosing of afatinib of 40 mg and less ([P10-09678](#)). The dose selection for this trial follows the above principle especially noting that the population in the trial will be naive to EGFR TKI, and with associated comorbidities from smoking history may be at risk for higher rate of discontinuation if a starting dose of 50 mg daily were chosen. Additionally, squamous cell NSCLC patients represent EGFR wt population that may benefit from intensifying maximal doses. Thus, in this trial development of afatinib will continue at a starting dose of 40 mg to optimize the tolerability and efficacy balance. The daily dose will be modified following careful monitoring of patient's drug-related adverse events and medication compliance; with option to dose-escalate to 50 mg for patients meeting the criteria specified in [Section 4.1.4.1](#).

The starting dose for erlotinib is 150 mg daily continuously in accordance with the Tarceva® package insert. In case of drug-related adverse events, the dose will be reduced to 100 mg and 50 mg daily, as described in [Section 4.1.4.2.1](#).

#### 4.1.4 Drug assignment and administration of doses for each patient

##### 4.1.4.1 Afatinib assignment and administration

Patients randomised to the afatinib arm will take a single oral dose of afatinib each day starting at a dose of 40 mg, continuously, until the development of progressive disease or

**Proprietary confidential information.**

© 2016 Boehringer Ingelheim International GmbH or one or more of its affiliated companies. All rights reserved.

This document may not - in full or in part - be passed on, reproduced, published or otherwise used without prior written permission.

unacceptable adverse events. Dose escalation and reductions can occur. See Sections [4.1.4.1.1](#) and [4.1.4.1.2](#).

The medication should be taken at the same time each day at least one hour before food intake and at least three hours after food intake. The tablet should be swallowed with a glass of water (250 mL).

Missed doses of afatinib can be made up during the same day, following the administration guidelines in the above paragraph. Otherwise, the dose must be skipped and patients should take the next scheduled dose at the usual time. Patient with emesis must not take a replacement dose.

Medication will be dispensed in bottles containing 30 tablets at the beginning of each treatment course. For administrative purposes, a treatment course is defined as 28 days. Treatment will start when the patient is randomized and stop when the patient is determined to have disease progression or for any reasons detailed in [Section 3.3.4.1](#). Study drug will be prescribed by the investigator and may be dispensed either by the investigator, site staff or affiliated pharmacy.

#### 4.1.4.1.1 Dose escalation for afatinib

The dose of afatinib administered may be escalated to 50 mg at the start of Course 2 if all of the following criteria are met during Course 1:

- Drug-related CTCAE grade  $\leq 1$  skin rash
- Absence of diarrhoea, mucositis, and/or any drug-related event (any grade) other than skin rash CTCAE  $\leq 1$
- Afatinib dose was not previously reduced due to any of the AEs depicted in the Dose reduction scheme [Table 4.1.4.1.2: 1](#)
- Compliant dosing of afatinib, as described in [Section 4.3](#)

Dose escalation is prohibited in any situation other than that prescribed above. The patient should remain on 50 mg unless dose reduction becomes necessary (see [Table 4.1.4.1.2: 1](#)).

#### 4.1.4.1.2 Dose reduction for afatinib

In the event of treatment-related toxicities, the treatment with afatinib should be handled according to the schedule in [Table 4.1.4.1.2: 1](#).

**Proprietary confidential information.**

© 2016 Boehringer Ingelheim International GmbH or one or more of its affiliated companies. All rights reserved.

This document may not - in full or in part - be passed on, reproduced, published or otherwise used without prior written permission.

Table 4.1.4.1.2: 1 Dose reduction scheme for afatinib

AE type and CTCAE Grade	Action	Dose reduction scheme

Events related to study drug:
 
 
• Diarrhoea Grade 2 persisting for 2 or more consecutive days (48 hours) despite adequate anti-diarrhoeal medication/hydration
 
• Nausea and/or Vomiting Grade 2 persisting for 7 or more consecutive days despite anti-emetic treatment/hydration
 
• Reduced renal function to <math>\geq</math> Grade 2 as measured by serum creatinine, proteinuria or decrease in glomerular filtration rate of more than 50% from baseline
 
• Any drug related AE Grade <math>\geq</math>3
 
	
Pause treatment until patient has recovered to Grade <math>\leq</math>1 or baseline.
 
Resume treatment at reduced dose according to schedule opposite.
 
If patient has not recovered to Grade <math>\leq</math>1 or baseline within 14 days study treatment must be permanently discontinued.
	
If patient was receiving 50 mg, resume treatment at a dose of 40 mg.
 
If patient was receiving 40 mg, resume treatment at a dose of 30 mg.
 
If patient was receiving 30 mg, resume treatment at a dose of 20 mg.
 
If patient was receiving 20 mg, discontinue afatinib.

Acute onset and/or unexplained worsening of pulmonary systems (dyspnea, cough, fever)
	
Pause afatinib while clinical assessment to exclude ILD is completed.
	
If ILD is ruled out as a cause of symptoms, grade symptoms and relatedness and report as AEs.
 
If AEs are not related, resume afatinib at current dose. If AEs are drug related, follow directions in row above.
 
If ILD is confirmed, discontinue afatinib

 Baseline is defined as the CTCAE Grade at the start of treatment

 In the event that the patient is deriving obvious clinical benefit according to the investigator's judgement, further treatment with afatinib will be decided in agreement between the sponsor and the investigator.

In the event of any unrelated adverse events, the investigator may choose to interrupt the medication for up to 14 days, but no dose reduction should occur. If the medication is interrupted for more than 14 days, the decision to continue with afatinib will be made by the

**Proprietary confidential information.**

© 2016 Boehringer Ingelheim International GmbH or one or more of its affiliated companies. All rights reserved.

This document may not - in full or in part - be passed on, reproduced, published or otherwise used without prior written permission.

investigator in agreement with the BI Clinical Monitor. Continuous dose interruption of >28 days is not allowed.

#### 4.1.4.2 Erlotinib

Patients randomised to the erlotinib arm will take a single oral dose of erlotinib each day starting at a dose of 150 mg, continuously, until the development of progressive disease or unacceptable adverse events. Dose reductions can occur. See Section 4.1.4.2.1. Erlotinib should be taken the same time each day, always one hour before food intake and two hours after food intake. Missed dose can be taken the same day at least one hour before or two hours after the ingestion of food. If daily dose is missed entirely, the regularly prescribed dose should be taken the next day. Do not double the dose of erlotinib.

For administrative reasons, treatment courses are 28 days (4 weeks). At the beginning of each treatment course, patients will be provided either a bottle containing 30 tablets of 150 mg or 100 mg erlotinib if the patients are receiving 150 mg or 100 mg of erlotinib, respectively, or 2 bottles containing 30 tablets in each bottle of 25 mg of erlotinib if the patients are receiving erlotinib 50 mg; or blister packs containing 30 tablets of either 150 mg or 100 mg erlotinib if the patients are receiving 150 mg or 100 mg of erlotinib, respectively, or a blister pack containing 60 tablets of 25 mg erlotinib if the patient is receiving 50 mg of erlotinib daily. Study treatment will be started at Course 1, visit 1 and will end when patient discontinues study drug due progressive disease progression or for any reasons detailed in [Section 3.3.4.1](#). Study drug will be prescribed by the investigator and may be dispensed either by the investigator, site staff or affiliated pharmacy.

##### 4.1.4.2.1 Dose reduction and discontinuation of erlotinib

In the event of treatment toxicities, the treatment with erlotinib should be handled according to the schedule in [Table 4.1.4.2.1: 1](#).

**Proprietary confidential information.**

© 2016 Boehringer Ingelheim International GmbH or one or more of its affiliated companies. All rights reserved.

This document may not - in full or in part - be passed on, reproduced, published or otherwise used without prior written permission.

Table 4.1.4.2.1: 1 Dose reduction and discontinuation scheme for erlotinib

AE type and CTCAE Grade	Action	Dose reduction scheme

 
• Diarrhoea Grade 2 persisting for 2 or more consecutive days (48 hours) despite adequate anti-diarrhoeal medication/hydration
 
• Ocular disorders Onset of ocular disorders requiring treatment intervention or <math>\geq</math>CTCAE Grade 3 OR worsening ocular disorders <math>>1</math> CTCAE Grade
 
• Dermatology/skin Any dermatology/skin CTCAE <math>\geq</math>Grade 3
 
• Total bilirubin <math>>3</math> x ULN and/or transaminases are <math>>5</math> x ULN in pts with normal baseline
 
• Total bilirubin <math>>3</math> x ULN in pts with hepatic impairment (total bilirubin <math>></math> ULN or Child Pugh A,B and C)
 
• Dehydration in patients at risk for renal failure
 
• Any drug related AE Grade <math>\geq 3</math>
 
	
Pause treatment until patient has recovered to Grade <math>\leq 1</math> or baseline.
 
Resume treatment at reduced dose according to schedule opposite.
 
If patient has not recovered to Grade <math>\leq 1</math> or baseline within 14 days study treatment must be permanently discontinued.
	
If patient was receiving 150 mg, resume treatment at a dose of 100 mg.
 
If patient was receiving 100 mg, resume treatment at a dose of 50 mg.
 
If patient was receiving 50 mg, discontinue erlotinib.

 
• Hepatic failure or gastrointestinal perforation
 
• Acute/ worsening ocular disorders more severe than allowed above for dose reduction
 
		Discontinue erlotinib

Proprietary confidential information.

© 2016 Boehringer Ingelheim International GmbH or one or more of its affiliated companies. All rights reserved.

This document may not - in full or in part - be passed on, reproduced, published or otherwise used without prior written permission.

Table 4.1.4.2.1: 1(continued) Dose reduction and discontinuation scheme for erlotinib

AE type and CTCAE Grade	Action	Dose reduction scheme
Acute onset and/or unexplained worsening of pulmonary systems (dyspnea, cough, fever)	Pause erlotinib while clinical assessment to exclude ILD is completed.	
If ILD is ruled out as a cause of symptoms, grade symptoms and relatedness and report as AEs.
 
If AEs are not related, resume erlotinib at current dose. If AEs are drug related, follow directions in row above.
 
If ILD is confirmed, discontinue erlotinib.

\* Patients taking erlotinib with an inhibitor of both CYP3A4 and CYP1A2 and experiencing a severe adverse reaction should be evaluated for a dose reduction of erlotinib.

 Baseline is defined as the CTCAE Grade at the start of treatment

 In the event that the patient is deriving obvious clinical benefit according to the investigator's judgement, further treatment with erlotinib will be decided in agreement between the sponsor and the investigator.

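### In the erlotinib dose table the pulmonary row's pointer lands on the stop-drug row, not on the pause-and-reduce row that was clearly meant

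*Protocol*

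**What the plan says.** Protocol Section 4.1.4.2.1 sets out erlotinib dose changes in a table with three rows.

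- **Row 1, pause and reduce.** The triggers are a list of specific toxicities and, as a general category, "Any drug related AE Grade" 3 or higher. Treatment is paused until recovery, and then: "Resume treatment at reduced dose according to schedule opposite". The schedule begins "If patient was receiving 150 mg, resume treatment at a dose of 100 mg" and ends "If patient was receiving 50 mg, discontinue erlotinib". A patient who has not recovered within 14 days stops, unless the exception in footnote 2 applies, under which "further treatment with erlotinib will be decided in agreement between the sponsor and the investigator".
- **Row 2, stop.** The triggers are liver failure, gut perforation and "Acute/ worsening ocular disorders more severe than allowed above for dose reduction". The action column is empty and the only direction is to stop erlotinib.
- **Row 3, pulmonary symptoms** (on the continued page). Erlotinib is paused while ILD is investigated. If ILD is excluded, the symptoms are graded and assessed for relatedness, and then: "If AEs are not related, resume erlotinib at current dose. If AEs are drug related, follow directions in row above". A separate branch reads "If ILD is confirmed, discontinue erlotinib".

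The afatinib table (Table 4.1.4.1.2: 1) uses the same sentence with the drug name changed. It has only two rows, so there the row above is the pause-and-reduce row.

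**The concern.** Row 3 sends a drug-related, non-ILD event to the row above, and that row is row 2. If the event is Grade 3 or higher, row 1 already covers it and gives the opposite instruction. One operative dosing table therefore gives two answers for the same patient, and only in the comparator arm.

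Protocol Section 5.2.1 assesses tolerability by dose reductions and by discontinuations due to adverse events, and SAP Section 7.8.1 tabulates the two separately. A site that follows the pointer literally moves a patient from the first table to the second. It also withdraws a drug that the plan means to continue at a lower dose.

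**Working it through.** No alpha, power or event count is involved. The check is to follow each route through the table, count the dose levels left, and see which route the rest of the protocol supports.

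**1. Row order.** The pulmonary row is the first row under the continued header, and the row before it is the stop row. The page break does not change the order. A reader who turns back for the row above meets the stop instruction first.

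**2. The two routes for erlotinib.** The levels are 150, 100 and 50 mg. The Grade 3 or higher columns count the lower levels still available to a patient who recovers within 14 days.

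| Dose at event | Grade 3 or higher: row 1 | Grade 3 or higher: literal pointer | Grade 1-2: row 1 | Grade 1-2: literal pointer |
|---|---|---|---|---|
| 150 mg | 2 (100, 50) | 0, stop | general bullet not triggered | stop |
| 100 mg | 1 (50) | 0, stop | general bullet not triggered | stop |
| 50 mg | 0, stop | 0, stop | general bullet not triggered | stop |

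At Grade 3 or higher the difference is 2 - 0 = 2 levels at 150 mg, 1 - 0 = 1 at 100 mg and 0 - 0 = 0 at 50 mg. In this grade range the routes differ only for patients on 150 or 100 mg who recover in time, or who would be kept on treatment under footnote 2. At Grade 1-2 they differ at every dose, including 50 mg, because the pointer carries no grade limit. Row 1's other bullets concern diarrhoea, eye, skin and liver findings and dehydration, so only its general Grade 3 bullet can reach a pulmonary symptom.

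**3. The same event on afatinib.** Here the row above is pause and reduce. At Grade 3 or higher, a patient on 50 mg keeps 3 lower levels (40, 30, 20), on 40 mg 2, on 30 mg 1 and on 20 mg 0. There is no conflict.

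**4. Which route was meant.**

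- Row 3 asks for grade and relatedness before it points elsewhere. Only row 1 uses grade and relatedness and gives stepwise directions.
- Row 3 stops the drug for confirmed ILD as a separate outcome. Under the literal pointer, drug-related events without ILD would end the same way and the distinction would lose its purpose.
- Section 4.1.3 and the Synopsis answer drug-related events on erlotinib with reduction to 100 and 50 mg.
- Section 4.2.1 (emergency procedures) deals with these same symptoms for both drugs. It requires interruption during the work-up and permanent withdrawal once ILD is diagnosed.
- Section 3.3.4.1 lists diagnosed ILD as a reason to stop and has no separate item for a drug-related pulmonary event without ILD.

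All of this supports row 1. The likely origin is a sentence shared with the afatinib table that was not adjusted for the additional stop row.

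**5. Number of patients.** Section 4.2.3 names dyspnoea and cough among the common adverse events on erlotinib but gives no frequency. Nothing in the documents says how many would be acute or worsening, drug-related and not ILD, so no count can be derived.

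**The case against.** The strongest reply is that this is a loose pointer with an obvious meaning. Row 1 as written covers any drug-related event of Grade 3 or higher, so a site that pauses and reduces is also following the table. The Synopsis and Sections 3.3.4.1, 4.1.3 and 4.2.1 point the same way. Sending a graded, drug-related cough to a row about liver failure and perforation would make the grading step pointless.

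Most of this stands. The intended meaning can be recovered, and it would be too strong to say that the table gives only the wrong instruction.

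Two things remain. Section 4.2.1 sends the reader back to the dose tables for details, so the body text does not itself correct the pointer. And for Grade 1-2 events row 1 offers no competing instruction: the patient is already paused under row 3, the literal pointer says stop, and no line in the table says to resume.

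A reader might go further and infer a deliberately harsher stopping rule for erlotinib, or a bias in the efficacy comparison. The documents do not support either. The identical afatinib sentence and the sections above show a drafting slip. The primary analysis is by randomised group whatever treatment was taken (Section 7.3.1), and tumour assessments continue after stopping for an adverse event (Section 3.1).

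**Conclusion.** The point holds as a minor internal inconsistency. Read literally, the pointer contradicts row 1 and Section 4.1.3 for drug-related, non-ILD pulmonary events of Grade 3 or higher. It would also stop erlotinib at every dose for drug-related Grade 1-2 pulmonary events.

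The cost per affected patient at Grade 3 or higher is two dose levels at 150 mg, one at 100 mg and none at 50 mg. The number of patients is unknown and may be zero, since many sites would infer row 1. Any effect on PFS or OS is likely negligible; this is a judgement that rests on few patients being affected, not a calculation. The realistic exposure is an unintended comparator-arm discontinuation, and inconsistent recording of the same event as a reduction or a discontinuation in tables that are descriptive.

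A reader might also infer that important protocol violations would be coded the wrong way round, because code C1 in SAP Section 6.2 covers doses not handled as the protocol directs. That goes too far. The list is described as a working one that may not be final until the blinded report planning meeting, no per-protocol set depends on it, and nothing suggests that patients would be coded against the protocol's evident sense.

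**What to change.** In Table 4.1.4.2.1: 1, replace the reference to the row above with an explicit reference to the first (pause-and-reduce) row, for events that meet that row's thresholds. Add one sentence: drug-related pulmonary events below those thresholds resume at the current dose once ILD is excluded.

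The afatinib pointer already leads to the right row and needs no correction. Using the same explicit wording there would keep the two arms alike, but it is optional.

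The cost is a line or two of text, by protocol clarification or site letter. No extra data, patients or analyses are needed.
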